8.1.1 Interim analysis

Patient inclusion is reported to the sponsor and shared between US and EU sponsor. EU sponsor has the responsibility to monitor the inclusion rate and in collaboration with the US sponsor announce when inclusion should be halted for interim analysis. After inclusion of 15 evaluable patients in each arm (comprising both US and EU trial), an interim analysis will be performed. A decision to continue in stage 2 will be based on pooled data of stage 1 in both the US and European trial. Each study arm may be closed separately after stage 1, if it does not reach the pre-specified responses. Decision to go to stage 2 will be made by a consortium consisting of US sponsor, EU sponsor, one investigator from each site in US and EU, and 1-2 Karyopharm representatives. In case 2 patients out of 15 patients derive clear clinical benefit according to a unanimous agreement among members of the consortium, a decision can be made to proceed to stage 2. Clear clinical benefit is defined as: non-progressive disease with improvement in tumor related symptoms and treatment is well tolerated.

The results of the interim analysis showed three responses out of fifteen patients in the thymoma cohort (3 according to ITMIC and 2 according RECSIST). Therefore, the thymoma cohort will be continued and additional 10 patients will be included across all EU and US sites.

No response was observed in the thymic carcinoma group. This cohort will be closed.

8.2 Statistical plan

8.2.1 Study populations

Thymoma

This population consists of all patients with thymoma who have received at least one dose of study drug on trial.

Thymic carcinoma

This population consists of all patients with thymic carcinoma who have received at least one dose of study drug on trial. This arm was closed as no response was observed within the fifteen patients.

Safety population

This population consists of all patients who have received at least one dose of study drug on trial.

8.2.2 Demographics and baseline characteristics

Demographics and baseline characteristics will be summarized separately for each cohort and will include at a minimum age, gender, diagnosis, performance status, and number of prior lines of therapy.

8.2.3 Analysis of primary endpoint

Analysis of ORR according to RECIST 1.1 will be reported with 95% CI. Each arm will be analysed separately.

8.2.4 Analysis of secondary endpoints

Analysis of time to event endpoints will be done using the Kaplan-Meier method. Median time and 95% CI will be reported.

8.2.5 Analysis of exploratory endpoints

Data from biomarker analysis will be treated as continuous or discrete variables as appropriate and correlated to response, time to event endpoints and safety endpoints using univariate and multivariate analysis. Biomarker data will be transformed prior to analysis as appropriate.

9 Administrative Matters

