2.2 Secondary Objectives

Secondary objectives of the study are

- To determine the efficacy of Selinexor in adults with TETs determined by overall response rate according to modified ITMIG response criteria.
- To determine the overall response rate of selinexor in patients with advanced thymomas.
- To determine six months PFS of patients with TET treated with selinexor.
- To determine overall survival of patients with TET treated with selinexor.
- To evaluate exploratory biomarkers for prediction of response to selinexor in patients with TET.
- To determine progression free survival in patients with advanced, inoperable TETs treated with selinexor
- To evaluate safety and tolerability of Selinexor.

3 Investigational Plan

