5.1.2 Translational and pharmacodynamics (PDn) analyses

Tumour Biopsies

Archived Tumour tissue may be obtained from before the first dose. Tissue may be tested for levels of expression and cellular localization (nuclear/ cytoplasm) of biomarkers of response including XPO1; representative XPO1 cargos such as: P53, SURVIVIN, FOXO1; markers of direct-tumour response such as the proliferation marker Ki-67 and the apoptotic marker Cl. Casp3 and potential predictive biomarkers by immunohistochemistry.

Tumour tissue obtained before treatment should be available as paraffin embedded-formalin fixed sample. Tumour samples may be stained by OHC for XPO-1 antibody and protein expression will be quantified. XPO-1 expression will be correlated with response to treatment.

Samples collected may be sequenced using NEXTGEN technology on our recently acquired MiSeq sequencer (Georgetown University). Patients who have no available tissue will be eligible for the trial. A custom-designed cancer-associated gene panel which includes all the identified recurrent mutations in thymic carcinomas, published cancer driver genes and COSMIC cancer gene census (<http://cancer.sanger.ac.uk/cosmic/census>) will be used for targeted sequencing [15-17]. Comparative sequencing analysis of the tumour/blood pairs will allow us to identify specific somatic mutations and the number of somatic mutations in a given tumour. In addition, samples may be sequenced for the identification of mutations in DNA damage repair genes such: ATM, ATR, BRCA1, BRCA2, CHEK1, CHEK2, FAM175A, GEN1, MRE11A, MSH2, MSH6, NBN, PALB2, PMS2, RAD51, ERCC1, MLH1. The data will be employed to evaluate the correlation between the type/number of mutations and patients' response to Selinexor therapy.

All biopsy-related studies will be performed at Georgetown Lombardi Comprehensive Cancer Center.

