8.1 Trial Design

This is a non-randomised, open label two armed phase II trial. Arm A includes patients with thymoma and arm B include patients with thymic carcinoma.

The primary objective of the trial is to determine the effect of selinexor in patients with inoperable thymoma and in patients with thymic carcinomas, previously treated with with at least one platinum containing chemotherapy regimen as determined by overall response rate according to RECIST 1.1.

The study is composed of two similar phase II trials conducted in the US and Europe. The final analysis will be performed on data pooled from both trials. The calculation of the total sample size is based on the pooling of data from both trials.

The following assumptions are the basis for the sample size:

- Simon's minimax design will be used
- A response rate of 10 % is considered clinical irrelevant.
- A response rate of 30 % is considered undesirable to overlook.
- Type one error rate: 0.05
- Power: 0.80
- Stage 1: 15 evaluable patients in each arm
- Stage 2: 10 evaluable patients in each arm
- For each arm: If response is observed in 2/15 patients in stage 1, accrual will continue in stage 2.
- For each arm: If response in 5 out of 25 patients, the alternative hypothesis is accepted and the drug is considered active and appropriate for further evaluation.

Included patients who are not evaluable for response will be replaced.

All patients receiving at least one dose of selinexor will be included in the final analysis of primary and secondary endpoints. However this is not an intention to treat (ITT) study.

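### Section 8.2.5 plans a multivariate analysis of biomarkers against response that about 3 to 8 thymoma responders cannot support, so any such model is likely to be overfitted

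*Combined protocol and SAP*

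**What the plan says.** Section 8.2.5 (Analysis of exploratory endpoints) states that biomarker data will be "correlated to response, time to event endpoints and safety endpoints using univariate and multivariate analysis". Its qualifier about appropriateness governs how variables are typed and transformed, not which models are fitted. The section gives no lead marker, covariate limit, penalisation or selection rule, multiplicity handling or validation step, and no other section supplies one.

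Section 5.1.2 lists six protein markers (XPO1, p53, survivin, FOXO1, Ki-67, cleaved caspase-3) and 17 DNA-repair genes, plus a custom gene panel of unstated size. Most of this testing is worded as optional, the cargo proteins and genes are given as examples, and patients without tissue remain eligible. Two statements are firmer: XPO1 expression is to be correlated with response, and for sequencing, "The data will be employed to evaluate the correlation between the type/number of mutations" and response.

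Section 2.2 lists the aim among the secondary objectives: "To evaluate exploratory biomarkers for prediction of response to selinexor in patients with TET". The synopsis does the same, but puts the parameter under exploratory parameters, still to be determined.

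Section 8.1 fixes the size of each arm: "Stage 1: 15 evaluable patients in each arm" and "Stage 2: 10 evaluable patients in each arm". Section 8.1.1 reports thymoma stage 1 results of 2/15 responses by RECIST and 3/15 by ITMIG, and no responses in thymic carcinoma, whose arm was closed.

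**The concern.** What limits a model for a binary outcome is the size of the smaller outcome group, here the responders. With so few, an ordinary logistic model with several markers either has no finite maximum-likelihood estimate, because the markers separate responders from non-responders perfectly, or gives an apparent accuracy that is mostly fitted noise. The protocol names prediction of response as an objective, so such a model would be reported as the answer to it. The tumour is rare (Section 1.1.1), so a chance predictor would be hard to refute and could influence which patients are selected for later work.

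**Working it through.** **1. The plan's own figure.** Inputs from Section 8.1: for the null rate, "A response rate of 10 % is considered clinical irrelevant"; for the alternative, the plan says that "A response rate of 30 % is considered undesirable to overlook"; the type I error is 0.05 and the target power is 0.80. An exact search for Simon's minimax design returns 15 patients in stage 1 and 25 in total, continuing at 2 or more of 15 and declaring success at 6 or more of 25, with type I error 0.033 and power 0.802. The sample size of 25 therefore reproduces. The written success rule of 5 of 25 gives 0.093 and 0.898; that is a separate matter and does not affect what follows. No size or power is stated for the biomarker analysis.

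**2. Responders available.**
- Expected among 25: 25 × 0.10 = 2.5; 25 × 0.30 = 7.5. That is about 3 to 8.
- Given stage 1 by RECIST: 2 + 10 × 0.10 = 3; 2 + 10 × 0.30 = 5.
- Given stage 1 by ITMIG: 3 + 1 = 4; 3 + 3 = 6.
- Thymic carcinoma adds 0. Optional tissue can only lower these counts.

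**3. Markers named.** 6 + 17 = 23, before the wider panel.

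**4. Responders per covariate.** With all 23: 3/23 = 0.13 to 8/23 = 0.35. At a lenient 5 responders per covariate (an assumption, not a document figure), the data support 3/5 = 0.6 to 8/5 = 1.6 covariates; two covariates would need 10 responders.

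**5. Multivariable logistic model on pure noise.** Simulated with 25 patients, all with tissue, and independent normally distributed markers unrelated to response. Separation was checked by linear programming.

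| Responders | 6 markers: median apparent AUC | 6 markers: separation | 10 markers: separation |
|---|---|---|---|
| 3 | 0.92 | 42% | 94% |
| 5 | 0.84 | 10% | 75% |
| 7 | 0.81 | 4% | 44% |

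Repeat runs differ by a few percentage points in separation and by about 0.02 in AUC. Even 2 noise markers give a median apparent AUC of 0.66 to 0.71, where the true value is 0.50.

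**6. Univariable tests of all 23 markers against response, no true effect.**
- Independent tests at exactly 5%: 23 × 0.05 = 1.15 false positives expected; 1 − 0.95^23 = 0.69 chance of at least one.
- Exact rank tests, all 23 markers continuous, 25 patients: 63% to 68%.
- 6 continuous markers plus 17 mutation markers at assumed prevalence 5% to 20%, 25 patients: 30% to 44%. Fisher tests on rare mutations are conservative.
- The same mixed set with tissue from only 15 patients (assumed): 21% to 42%.

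The overall range is roughly 20% to 70%. The best of 23 continuous noise markers, taken alone, has a median apparent AUC of 0.88, 0.81 or 0.77 for 3, 5 or 8 responders.

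**The case against.** The strongest reply is that the plan commits to little. Testing is optional, the lists are examples, the parameter is still to be determined, and a multivariate analysis could mean one with two covariates. If only XPO1 expression and mutation number were used, with 5 or 7 responders, the chance of any false p<0.05 is about 8%, separation is at most 0.3%, and the median apparent AUC is about 0.66. The work is labelled exploratory and no trial decision depends on it.

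Much of this stands, and it rules out several stronger readings that a reader might infer:

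- **Spurious predictors are near certain.** Crossing 23 markers with three outcome families gives 69 tests, hence 69 × 0.05 = 3.45 false positives and 1 − 0.95^69 = 0.97. This assumes 69 independent tests at exactly 5%. The outcomes come from the same patients, and tests on rare mutations fall below 5%. The documents do not commit to testing all 69.
- **The model will fit perfectly.** Separation in 100% of runs with 23 markers, and the 10-marker rates above, assume continuous markers. With 3 continuous and 7 binary markers (assumed prevalence 0.1 to 0.2), separation falls to 8% to 50%. The plan does not say how many markers enter a model.
- **The trial's conclusion is at risk.** Activity is judged on response rate, which this analysis does not touch.
- **Every biomarker model fails equally.** Time-to-event and safety outcomes may have more events, up to about 25 in thymoma, enough for a few covariates.

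The reply does not rescue a multivariable model of response. Section 8.2.5 states that multivariate analysis will be used and sets no cap. The exploratory label neither makes such a model estimable nor says that its results are only hypothesis-generating.

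**Conclusion.** The concern holds for response. With about 3 to 8 responders the data support roughly one covariate, so a multivariable response model is likely, though not certain, to be overfitted. Apparent discrimination of about 0.81 to 0.92 from six noise markers shows the size of the problem. Univariable screening of all 23 named markers carries a roughly 20% to 70% chance of at least one false finding, depending on marker type and tissue yield.

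These figures assume no true associations, independent markers, the stated mutation prevalences, and continuous markers in the model simulations. The actual number of markers is unknown. This is a change the sponsor should make at low cost; it is not a threat to the trial.

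**What to change.** Revise Section 8.2.5 as follows.

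1. Drop the multivariable model for response, or limit it to a single-covariate penalised estimate. A two-covariate model or an optimism-corrected AUC would not be reliable with this many responders either.
2. Name XPO1 expression as the lead marker. Section 5.1.2 already commits to correlating it with response.
3. Report all other markers univariably, with estimates and 95% CIs. State how many markers and tests were performed, and give multiplicity-adjusted or false-discovery-rate values beside the nominal p-values.
4. Label the results hypothesis-generating, and bring the synopsis and Section 2.2 into line with the exploratory heading of 8.2.5.

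The cost is SAP wording and a little programming, with no extra patients, samples or visits. The downside is that fewer markers will be called nominally significant.

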9.1 Data Safety Monitoring Plan

The Georgetown Lombardi Comprehensive Cancer Center will be responsible for the data and safety monitoring of this multi-site trial. As this study is an investigator initiated study Phase II study utilizing a non-FDA approved drug for which the PI holds the IND it is considered a high risk study which requires real-time monitoring by the PI and study team and quarterly reviews by the LCCC Data and Safety Monitoring Committee (DSMC).

The Principal Investigator and the Co-Investigators will review the data including safety monitoring at their weekly institution based disease group meetings and on monthly disease group teleconferences.

All Severe Adverse Events (SAEs) are required to be reported to the IRB. Based on SAEs, the IRB retains the authority to suspend further accrual pending more detailed reporting and/or modifications to further reduce risk and maximize the safety of participating patients.

Progress on the trial and the toxicities experienced will be reviewed by the LCCC Data and Safety Monitoring Committee every 4 months from the time the first patient is enrolled on the study. Results of the DSMC meetings will be forwarded to the IRB with recommendations regarding need for study closure.

DSMC recommendations should be based not only on results for the trial being monitored as well as on data available to the DSMC from other studies. It is the responsibility of the PI to ensure that the DSMC is kept apprised of non-confidential results from related studies that become available. It is the responsibility of the DSMC to determine the extent to which this information is relevant to its decisions related to the specific trial being monitored.

A written copy of the DSMC recommendations will be given to the trial PI, Karyopharm Therapeutics, Inc. (drug supplier) and the IRB. If the DSMC recommends a study change for patient safety or efficacy reasons the trial PI must act to implement the change as expeditiously as possible. In the unlikely event that the trial PI does not concur with the DSMC recommendations, then the LCCC Deputy Director must be informed of the reason for the disagreement. The trial PI, DSMC Chair, and the LCCC Deputy Director will be responsible for reaching a mutually acceptable decision about the study and providing details of that decision to the IRB. Confidentiality must be preserved during these discussions. However, in some cases, relevant data may be shared with other selected trial investigators and staff to seek advice to assist in reaching a mutually acceptable decision.

If a recommendation is made to change a trial for reasons other than patient safety or efficacy the DSMC will provide an adequate rationale for its decision. If the DSMC recommends that the trial be closed for any reason, the recommendation will be reviewed by the LCCC Deputy Director. Authority to close a trial for safety reasons lies with the IRB, with the above described input from DSMC and the LCCC Deputy Director.

9.2 Collaboration with Other Institutions (in the US and EU)

This study (US) will be conducted in collaboration with Hackensack University Medical Center. [name] is the US Principal Investigator for the study and will oversee the study including the data gathering, safety and reporting. [name] will be the main study contact at Hackensack University Medical Center. Patients will be recruited at all institutions for the study.

Monthly conference calls will be conducted between all institutions to follow up on the progress of the trial. [name] will be responsible for coordination of the trial between all institutions. Study coordinators will notify [name] upon the accrual of any patients in any institution.

Monthly teleconferences will also be conducted between the centers in the US and those in Europe. An update of each center will be provided in writing and detailed in terms of US and EU participation. Accrual, safety and activity will be discussed in detail during these teleconferences.

9.2.1 Personnel

At each site, personnel dedicated to this protocol will be:

- A study PI
- A research coordinator
- A data manager

In addition, at Lombardi-Georgetown, there will be a dedicated “multi-institutional” research coordinator who will play the primary role in coordinating the trial between Lombardi-Georgetown and additional sites. This coordinator will be the main point of contact for [name] and the other site PIs for any study related concerns, and to screen each patient being considered for enrollment (Including “remote” screening for the patients being screened at other sites). This coordinator will also be the point of contact for the data managers for data entry questions. Finally, this coordinator will play a major role in regulatory coordination of the study, specifically by: 1) Reviewing and confirming all study-related adverse events; 2) Submitting all SAE reports to the Georgetown IRB (The research coordinators at the other sites will prepare SAE reports for patients treated at their respective sites, but the “multi-institutional” coordinator will submit the final report); 3) Gathering and preparing primary source data for review/audit.

9.2.2 Patient Enrollment

Enrollment at the sites will be competitive. If a patient is being screened for enrollment, the local research coordinator must send an email within 24 - 48 hours containing the subject number, to the PI, and to the multi-institutional coordinator. If a patient is successfully screened, the local research coordinator must send all supporting documentation to the multi-institutional research coordinator. Patients should not start therapy until both PI and the multi-institutional coordinator have reviewed the patient's records and confirmed that the patient is indeed eligible for enrollment.

9.2.3 Conference Calls

A monthly conference call will be held between Lombardi-Georgetown and the other sites to review patient enrollment, toxicity, and response assessment.

9.3 Data Management

Patient data will be entered into the on-line accessible Oracle Clinical database. This database is housed at Georgetown, but is accessible anywhere there is internet access. All research coordinators and data managers will attend an on-line training session to learn how to accurately enter any data into the Oracle database. All screening data should be entered prior to starting therapy, and all ongoing patient data should be entered within one week of each patient visit. The LCCC QA Manager will be reviewing all online data on a regular basis to ensure compliance.

9.4 Regulatory and Ethical Compliance

This clinical study was designed, shall be implemented and reported in accordance with the ICH Harmonized Tripartite Guidelines for Good Clinical Practice, with applicable local regulations (including European Directive 2001/20/EC and US Code of Federal Regulations Title 21), Division 5 of the Health Canada Food and Drug Regulations - Drugs For Clinical Trials Involving Human Subjects, and with the ethical principles laid down in the Declaration of Helsinki.

9.5 Institutional Review Boards/Ethics Committees

The protocol and the proposed informed consent form must be reviewed and approved by a properly constituted Institutional Review Board (IRB) before study start. Prior to study start, the Investigator is required to sign a protocol signature page confirming his/her agreement to conduct the study in accordance with these documents and all of the instructions and procedures found in this protocol and to

give access to all relevant data and records to the Sponsor, Quality Assurance representatives, designated agents of the Sponsor, IRBs/IECs/REBs and regulatory authorities as required.

9.6 Regulatory Authority Approval

Before implementing this study, the protocol must be approved by the FDA.

9.7 Protocol Adherence

Investigators attest they will apply due diligence to avoid protocol deviations. All significant protocol deviations will be recorded and reported in the final clinical study report (CSR).

9.8 Amendments to the Protocol

Any change or addition to the protocol can only be made in a written protocol amendment, and approved by the FDA where required, and the IRB. Only amendments that are required for patient safety may be implemented prior to IRB approval. Notwithstanding the need for approval of formal protocol amendments, the investigator is expected to take any immediate action required for the safety of any patient included in this study, even if this action represents a deviation from the protocol. In such cases, the PI should be notified of this action and the IRB at the study site should be informed according to local regulations but not later than 10 working days.

